2.4.1.3 Patient Participants

1. Be 18 years or older
2. Treated in the ED during study screening hours
3. Meet DSM-5 diagnostic criteria for moderate to severe opioid use disorder
4. Have a urine toxicology test that is positive for opioids (opiates, oxycodone, buprenorphine, or methadone). For patients with acute pain conditions requiring opioid administration, urine will need to be obtained prior to ED opioid medication administration.

2.4.1.4 Focus Group Participants

Providers, staff, and patients in EDs, office-based practices, and community-based programs will be included who are:

1. 18 years or older
2. Able to provide verbal informed consent

ED patients will include those previously enrolled during either Evaluation Period.

2.4.2 Exclusion Criteria

2.4.2.1 Patient Participants

1. Have a medical or psychiatric condition that requires hospitalization at the index ED visit
2. Be actively suicidal or severely cognitively impaired precluding informed consent
3. Present from extended care facility (e.g., skilled nursing facility)
4. Require continued prescription opioids for a pain condition
5. Be a prisoner or in police custody at the time of index ED visit
6. Currently have (past 30 days) been enrolled in formal addiction treatment for OUD, including by court order
7. Inability to provide reliable locator information including two contact numbers
8. Be unwilling to follow study procedures (e.g., unwilling to provide permission to contact referral provider/program or return for 30-day assessment)
9. Have prior enrollment in the current study. Note: A patient may **NOT** enroll in both the BEP and IFEP.

10. Not able to speak English sufficiently to understand the study procedures and provide written informed consent to participate in the study

3.0 GENERAL ANALYSIS DEFINITIONS AND CONVENTIONS

3.1 Patient Participant Analysis Populations

3.1.1 Pre-screened Population

The pre-screened population consists of all patient participants who present in the ED during screening hours.

3.1.2 Screened Population

The screened population consists of all patient participants who provided verbal consent at the initiation of the screening process.

3.1.3 Intent-to-Treat Population

The intent-to-treat (ITT) population consists of ED patients who provided informed consent and enrolled in the study. Data from ITT population will be used to evaluate the primary implementation outcome, primary effectiveness outcome, secondary effectiveness outcomes, and rates of enrolled patient participants receiving an appointment for opioid treatment provider/program upon ED discharge as part of secondary implementation outcome measures. Note that participants who enrolled in the study but were subsequently determined to have been ineligible are *not* included in the ITT population.

3.1.4 Safety Population

The safety population includes all patient participants who provided informed consent during the screening visit. This includes enrolled patient participants that were later found to be ineligible.

3.2 Other Populations

3.2.1 Survey Participant Population

The survey population includes all provider participants who were enrolled in the study and who completed at least one IF survey.

3.2.2 Focus Group Participant Population

The focus groups population includes all individuals who participated in at least one focus group.

3.3 General Definitions

3.3.1 Index ED Visit

The Index ED Visit is the first visit for patient participants and involves both screening and enrollment for each evaluation period.

3.3.2 Follow-up Visit

The Follow-up visit date is defined as the 30th day estimated post-index ED Visit discharge. The actual visit can occur later, but information is only collected about events that occurred within 30 days of the index ED visit discharge date.

3.3.3 IF Survey Dates

The baseline survey will occur toward the end of the BEP. This will be followed by two more survey visits (Follow-up Survey 1 and Follow-up Survey 2) that will occur at the beginning and toward the end of the IFEP.

3.3.4 Study Day

Study Day is defined as the number of days post-index ED Visit with Study Day 0 defined as the date eligibility confirmed which is collected on the enrollment forms for segments B and C (i.e., EC0069B, EC0069C).

3.3.5 Safety Window

As buprenorphine is an FDA approved marketed medication with known and labeled adverse events, safety events are only recorded on the AE/SAE form within the 30-day follow-up period and not followed to resolution. The safety window for this study is, generally, from 30 days prior to the index ED visit to Study Day 30. For ED visits and hospitalizations, suicidal ideation, and overdoses, the window is 30 days prior to the index ED visit for baseline and from baseline to Study Day 30 for the follow-up visit. Deaths occurring prior to Day 30, whether the site identifies on their own or the information was provided by NDI, are included. Should the site learn of a death (aside from NDI) after Study Day 30 and before the follow-up visit occurred, then this will be reported on the STC.

3.3.6 Calendar Time

Calendar time for analysis is defined as the number of days since the site opened for enrollment in the baseline evaluation period. Below are the start and end dates for each site in each evaluation period. The start date is defined as the date the site was given access to the eClinical system to begin enrolling participants in the study for that particular evaluation period. The end date is defined as the last day the site was able to enroll participants in the EDC system for each evaluation period. Note that during the IFEP, enrollment was paused due to the COVID-19 public health measures put into place at two sites, Harborview Medical Center and University of Cincinnati. The days enrollment was paused will be considered as part of the primary analysis and several sensitivity analyses will be performed to account for this pause.

Site	Baseline Evaluation Period		IF Evaluation Period			
	Start Date	End Date	Start Date	Date Paused for COVID-19	Date Reopened for COVID-19	End Date
MA Johns Hopkins ED	4/10/2017	4/9/2018	10/9/2018	N/A	N/A	10/8/2019
NY Mount Sinai ED/Beth Israel	7/6/2017	7/5/2018	1/4/2019	N/A	N/A	1/5/2020
OV University of Cincinnati ED	10/9/2017	10/8/2018	4/8/2019	03/13/2020	6/10/2020	7/6/2020
PNW Harborview Medical Center ED	1/2/2018	1/1/2019	7/2/2019	03/3/2020	6/6/2020	10/4/2020

3.4 Table, Figures and Listings Conventions

All summary analyses described in this document for patient participants will be summarized by evaluation period and/or by site. Focus group data will be summarized by site for each individual wave (first month of IF, four to five months of IF, and near completion of IF period) and overall (the three waves combined) for the following categories: 1) patients, 2) providers and 3) all focus group participants combined. For IF provider surveys, respondent characteristics, Readiness

Ruler scores, and ORCA scores will be summarized by site, assessment period (Baseline, Follow-up 1 and Follow-up 2), and provider type (i.e., ED versus community provider). For all populations, descriptive statistics for continuous variables will be presented with mean, standard deviation, minimum, 25th percentile, median, 75th percentile, and maximum. Categorical variables will be summarized in terms of percentages and frequencies.

4.0 PARTICIPANT ENROLLMENT, DISPOSITION, AND FOLLOW-UP VISIT ATTENDANCE

4.1 Participant Enrollment

4.1.1 Patient Participant Enrollment

Proposed versus actual patient participant enrollments, under the assumption that 10 patient participants were expected to be enrolled per month per site, will be summarized by site and evaluation period in a tabular fashion and graphically. A flow diagram of patient participants will be presented that includes information on ineligibility and loss to follow-up for each evaluation period. Number of screen failures and reason for failure will be summarized by site and evaluation period as well. Number of ineligible patient participants that were enrolled will also be summarized by site and evaluation period.

4.2 Participant Disposition

4.2.1 Patient Participant Disposition

The number of patient participants who terminated early from the study along with the reasons for early termination will be summarized by site. Patient participants are defined as study completers if the Day 30 follow-up visit is completed as noted on the Study Completion (STC) form (i.e., STCOMPLT='1' or STLTEFUP='1'); they are considered non-completers if the visit is not completed (i.e., STCOMPLT='0' and STLTEFUP='0'). Patient participant disposition will be summarized by evaluation period for the number of patient participants completing the study, number of patient participants who completed the study within the window for the Day 30 follow-visit, the number of patient participants non-completed from the study, and the reasons for non-completion.

4.2.2 Provider Participant Disposition

The number of survey participants who completed each survey will be summarized by site. Survey participants are defined as completers if they completed the Site Characteristics form; they are considered non-completers if the form is not completed. Survey participants from an ED must complete the Site Characteristics-ED (SC1) form, survey participants from an OTP must complete the Site Characteristics – OTP Page 3 (SC4) form, and survey participants from a Community site must complete the Site Characteristics – Community Page 2 (SC6) form.

4.2.3 Focus Group Disposition

The number of focus group participants who completed each wave will be summarized by site.

4.3 Follow-up Visit Attendance

Attendance at the 30-day follow-up visit will be summarized by presenting the number and percentage of participants who attended by site and evaluation period. The visit is considered attended if the Engagement in Treatment: Participant form is completed.

5.0 ANALYSIS OF PARTICIPANT BASELINE CHARACTERISTICS

5.1 Patient Participant Baseline Characteristics

Demographics and characteristics such as sex, age, ethnicity, race, education completed, marital status, employment, timeline follow-back self-reported substance use, urine drug screen (including buprenorphine and fentanyl positivity), whether index ED visit was opioid-related, overdose events and EQ-5D-3L (i.e., EuroQol-5D) will be summarized by site and evaluation period. Since it is expected that participants with similar demographic characteristics will be enrolled during both evaluation periods, statistical comparisons of evaluation periods with respect to characteristics will be informal. If differences between evaluation periods are suspected, statistical testing will be performed.

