Program Marketing will be conducted to promote awareness of the ED-initiated BUP clinical practice among all emergency providers and other ED providers, patients and community physician ED referrals, once we have completed the IF period in each site. The goal of the marketing will be to promote ED-initiated BUP with referral for ongoing MAT, and designed to initiate a motivational discussion between patients and providers. The ultimate marketing approach will be tailored to the needs of the stakeholders and include direct (e.g., "in-services" to discuss the treatment services and referral processes, flyers) and indirect (e.g., informal conversation) approaches. We will work with ED leaders and community based providers and programs to sustain all projects and spread the learning to other spokes related to the institutions, including newsletters, etc.

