12.5 Hypothesized Treatment Effect Sizes

We anticipate that during the baseline evaluation period, the rates of ED-initiated BUP treatment for OUD (primary implementation outcome) will be very low at each of the study sites (less than 15% of all eligible patients). Based on our prior work and other published research, we estimate that the rates of participation in a formal addiction treatment on the 30th day post enrollment (effectiveness outcome) will be approximately 25% for patients with OUD enrolled in the baseline evaluation period.

We anticipate that during the IF evaluation period, at each of the study sites, at least 25% of all eligible patients with OUD will receive ED-initiated BUP with referral for ongoing MAT. Based on our prior research, we also anticipate that approximately 40-50% of patients with OUD enrolled during the IF evaluation period will be engaged in formal addiction treatments at 30 days. The expected treatment effects of this section are summarized in Table 3 below.

12.5.1 **Table 3:** Hypothesized Probabilities of Success

Outcome	Baseline Evaluation Period	IF Evaluation Period
Implementation	< 15%	25%
Effectiveness	25%	40-50%

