12.6 Power Analyses to Justify Sample Size

The power simulation to assess the adequacy of the sample size followed the method of Parzen⁵⁷ to simulate many vectors of (0,1) random variates with specified probabilities, a specified positive intraclass correlation (ICC) ρ , and assuming 240 patients enrolled at each of the 4 sites. The first 120 elements of each vector all had a common probability p_1 , while the second 120 elements had a common probability p_2 , where (p_1, p_2) are assumed probabilities of success in the baseline and IF evaluation periods, respectively. Each vector thus specifies in its first half a site's outcomes in the baseline evaluation period, while in the second half it specifies outcomes in the IF evaluation period. Four such vectors (one for each site) comprised the data for a single iteration of the simulation. Each element in each vector was assigned a month using the Study Timeline, shown in Figure 2¹. (However, month by itself played no role in determining the probability of success of

¹ Treatment assignment is partially confounded with time of enrollment in the proposed design. If scheduling does not go the way it is supposed to (e.g., if site 1 IF period onset is delayed by 3 weeks), confounding will be complete.

any vector elements.) For each setting of the parameters (p_1, p_2, ρ) , we generated 10,000 replicates (that is, 40,000 vectors) for simulation analysis.

The Stepped-Wedge model described in section 12.14.1 was used to analyze simulated data. Simulated power was taken to be the proportion of the 10,000 glimmix runs that had a significant type 3 p-value for arm (in this document the baseline and IF evaluation periods are referred to as “arms”) at level 0.05, one-tailed. There is no attempt to control for type I error across these two outcomes.

We simulated power for four parameter sets (scenarios), under both alternative and null hypotheses as indicated in Table 4.

12.6.1 **Table 4:** Scenarios Used to Simulate Power

Scenario	Hypothesis	P1 (Baseline)	P2 (IF)
Implementation outcome with low p1	Alt	0.05	0.25
Implementation outcome with high p1	Alt	0.15	0.25
Efficacy outcome with low p2	Alt	0.25	0.40
Efficacy outcome with high p2	Alt	0.25	0.50
Implementation outcome with low p1	Null	0.05	0.05
Implementation outcome with high p1	Null	0.15	0.15
Efficacy outcome	Null	0.25	0.25

12.7 Potential for Sites to have Baseline Probability of 0 for Primary Implementation Outcome

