2.3.3 Randomization and Blinding

Randomization does not occur at participant level. Five months before the start of a new step in the stepped wedge design, one site from those still in the BEP will be randomly selected to switch over to the IF period. The DSC performed this randomization and notified the LN via email of the site selected.

In an attempt to institute blinding and conduct an accurate BEP, ED provider participants, other than the site PI, were not notified of the intent of the study or the plan for an IF or IFEP. Patient participants were not notified of the intent of the study with respect to IF or IFEP. Research Assistants were notified of the intent of the IF and IFEP as each site transitioned to IF.

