7.2 Analysis of the Primary Implementation Outcome Measure

For the primary implementation outcome measure, a Generalized Linear Mixed Model will be used to compare the rates of provision of ED-initiated BUP with referral for ongoing MAT between the baseline and IF evaluation periods. The model for the primary analysis will be used to compare the rates of ED-initiated BUP with referral for ongoing MAT between the IFEP and the BEP is:

$$\text{logit}(p_{si}) = \alpha + \beta t_{si} + \gamma f_{si} + r_s$$

where

- p_{si} is the probability of success of patient participant i at site s ,
- t_{si} is the calendar time of enrollment of patient participant i at site s ,
- f_{si} is the indicator of whether patient participant i at site s is in the BEP ($f_{si}=0$) or IFEP ($f_{si}=1$), and
- r_s is the random effect of site s , where $r_s \sim N(0, \sigma^2)$.

In this model the γ estimate represents the estimated difference in the logit of the probability of success and captures the effect of implementation facilitation. Note that calendar time is measured in days and defined in Section 3.3.6. The model will test a one-tailed hypothesis at the 0.05 level. The null and alternative hypotheses are:

$$H_0: \gamma \leq 0$$

$$H_a: \gamma > 0.$$

The following SAS code fragment estimates this model:

```
proc glimmix data = primout method = quad;
  class arm (ref="1") site;
  model z = arm time / dist = binomial link = logit solution;
  random intercept / subject = site;
  estimate "trt effect" arm 1 -1 / cl;
  lsmeans arm / cl ilink;
run;
```

where

- primout is the dataset containing the variables required for the primary outcome analyses;
- arm is 1 for the BEP and 2 for the IFEP;
- z is an indicator of the ED-initiated BUP (primary implementation outcome measure); and

- time is defined in Section 3.3.6.

The main focus for estimation is the estimated Risk Difference (RD) defined as the difference between IFEP and BEP success rates, ($p_{IFEP} - p_{EP}$) with its 95% credible interval (CI). The estimated RD and its 95% CI will be obtained using the Bayesian approach outlined in the protocol Appendix 19.0 and in this SAP. Below is the SAS code used for analyzing the primary implementation outcome for this model:

```
proc mcmc data = simmsimul nbi = 1000 nmc = 10000 thin = 2 seed = 159  
monitor =(alpha-gammacoeff gammacoeff_gt_0 p1 p2 pdiff) statistics = (summary  
intervals);  
  parms alpha-gammacoeff 0;  
  parms sigma2 1;  

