7.5 Supportive Analyses of the Primary Outcome Measures

7.5.1 Subgroup Analyses

The NIH requires subgroup analyses by sex, race, and ethnicity (NIH, 2016). Analyses will be conducted by evaluation period. Primary implementation and effectiveness outcomes will also be summarized by these subgroups and evaluation period.

Several covariates may influence the primary implementation and effectiveness outcome measures. The GLMM models proposed for the primary outcomes will be expanded to adjust for potential effect modifiers. The models will be adjusted for sex, race, and ethnicity as well as each of their interactions with treatment. Below is a mathematical formulation of the models:

$$\begin{aligned} \text{logit}(p_{si}) = & \alpha + \beta t_{si} + \gamma f_{si} + \theta_1 \text{sex}_{si} + \theta_2 \text{race}_{si} + \theta_3 \text{ethnicity}_{si} \\ & + \theta_4 f_{si} * \text{sex}_{si} + \theta_5 f_{si} * \text{race}_{si} + \theta_6 f_{si} * \text{ethnicity}_{si} + r_s \end{aligned}$$

where sex, race, and ethnicity are indicators for their respective variables. They will be entered into the model in a stepwise manner using a p-value cutoff of 0.05. Note that an interaction term will always be included with its corresponding main effects, and the effect of treatment period will be forced into the model. If there are convergence issues, the model will be fit with each demographic factor separately. A forest plot will summarize the estimated risk difference from models where each demographic factor is considered separately to evaluate potential in trends in effect modification, which may not be statistically significant at the 0.05 level.

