7.7 Exploratory Analyses

We will also evaluate a limited set of patient and provider characteristics for their potential effect on successful implementation and effectiveness outcomes. Study participant characteristics to be evaluated are:

- Gender
- Race/Ethnicity
- Health insurance status
- Age
- Primary drug (heroin vs prescription opioids)
- Reason for presentation such as seeking treatment for OUD or overdose

- Referral to office-based BUP provider versus OTP
- Pain Intensity and Interference (PEG scale)
- Opioid overdose at index visit
- Stimulant positive urine toxicology, or self-report at index ED visit
- Fentanyl positive urine toxicology at index ED visit

ED characteristics such as size, location, existing substance abuse services and follow up resources as well as the range and number of addiction treatment services in the catchment area of the ED will be described, as well as ED provider characteristics such as age, gender, years, and level of training will be evaluated.

These analyses will utilize similar models as for the primary analysis, the MIXED models procedure repeated measures and generalized estimating equations (GEE), or other appropriate regression, clustering, and factor analytical tools to evaluate potential impact of site factors and patient characteristics on the primary implementation outcome and effectiveness outcome.

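### Neither primary model adjusts for patient case mix between the two periods; add one supportive model per outcome with forced, already collected covariates.

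*SAP*

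**What the plan says.** SAP 2.3.3 states that randomisation is not at participant level, and the eligibility criteria bar a patient from enrolling in both periods. The period effect therefore compares two separate groups of people.

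The primary models in SAP 7.2 and 7.4 contain evaluation period, calendar time and a random site effect. The Revised SAP (Analytic Model Adjustments) drops time and makes site fixed, leaving site and period. None of these models has a patient covariate. The one committed patient-level adjustment of the period effect is in the supportive section, SAP 7.5.1: "The models will be adjusted for sex, race, and ethnicity as well as each of their interactions with treatment", with stepwise entry at p < 0.05.

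On comparability, SAP 5.1 says: "Since it is expected that participants with similar demographic characteristics will be enrolled during both evaluation periods". Comparisons are to be informal, with testing only if differences are suspected, and nothing follows for the model. The sentence is about demographics; 5.1 also summarises substance use, urine results, opioid-related visit and overdose by period.

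Two features bear on who is enrolled after the switch. Program marketing (Protocol 11.10), carried out once a site's IF period is complete, is meant to "promote awareness of the ED-initiated BUP clinical practice among all emergency providers and other ED providers, patients and community physician ED referrals". SAP 2.3.3 adds: "Research Assistants were notified of the intent of the IF and IFEP as each site transitioned to IF".

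Reason for ED visit is collected on the Health Status form (Protocol 10.2.10) and insurance on the demographics forms (10.2.5). In the SAP, "Reason for presentation such as seeking treatment for OUD or overdose" and insurance are listed only as exploratory characteristics (7.7). The Table 11 shell has a row for OUD severity but none for reason for visit or insurance.

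**The concern.** Each site contributes a before/after contrast. If the share of patients likely to receive BUP, or likely to be in treatment at Day 30, differs between periods, that difference enters the period coefficient and is read as an effect of IF. Testing baseline differences does not remove it, and three demographic covariates help only so far as they track the factor that moved.

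Reason for visit is the obvious candidate. Treatment-seeking is not an exclusion, marketing addresses patients, and the research staff who screen and consent know which period they are in. At stake is whether a positive result can be read as changed ED practice or might partly reflect changed patients. The plan has no analysis that separates the two.

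**Working it through.** **Inputs from the documents.** "The model will test a one-tailed hypothesis at the 0.05 level" (SAP 7.2; the same rule is in 7.4). "assuming 240 patients enrolled at each of the 4 sites" (Protocol 12.6), so 4 × 120 = 480 per period. Planning rates (Protocol 12.5 and Table 4): BUP 5% or 15% rising to 25%; engagement 25% rising to 40–50%.

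**Inputs assumed.** The documents give neither the size of any case-mix shift nor its prognostic strength. I take a binary factor present in 20% of baseline enrolees, an outcome odds ratio (OR) of 4, a rise of 10 or 20 points in its share, and no IF effect. The wider range is OR 2–8 and rises of 5–30 points.

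**Step 1: the plan's own figure.** The plan states power above 0.8 for 5% vs 25% and 25% vs 50% at ICC below 0.3, and lower power for the other two scenarios. Wald power is P(Z > 1.645 − d/√(V·VIF)), where d is the logit difference, V = 1/[480·p1(1−p1)] + 1/[480·p2(1−p2)], and VIF allows for the overlap of period and month in the planned timeline (4.5 pooled, 7.8 within site). For 5% vs 25%, d = 1.846 and V = 0.0550, giving 0.98 and 0.88. The planned mixed model was also simulated with beta-distributed site rates, as the cited simulation method is not given in full (400 replicates for the first row, 200 for the others).

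| Scenario | Wald, VIF 4.5 / 7.8 | Simulated, ICC 0 to about 0.3 |
|---|---|---|
| 5% vs 25% | 0.98 / 0.88 | 0.955–0.998 |
| 25% vs 50% | 0.98 / 0.88 | 0.935–0.995 |
| 15% vs 25% | 0.57 / 0.39 | 0.48–0.60 |
| 25% vs 40% | 0.75 / 0.55 | 0.65–0.77 |

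The stated bound reproduces. These powers assume the same kind of patient in both periods.

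**Step 2: apparent rate from a case-mix shift alone.** Rate = s·r1 + (1−s)·r0, with r0 and r1 fixed by the baseline rate and OR 4.
- BUP, baseline 15%: r0 = 0.107, r1 = 0.323. At s = 0.30 the rate is 0.30 × 0.323 + 0.70 × 0.107 = 17.2%; at s = 0.40 it is 19.3%.
- Engagement, baseline 25%: r0 = 0.191, r1 = 0.486. The rates are 27.9% and 30.9%.

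**Step 3: false-positive rate of the final model.** For BUP at +10 points, z = 0.0217/√(2 × 0.161 × 0.839/480) = 0.91 and P(Z > 1.645 − 0.91) = 0.23. Simulation of the fitted models (2,000 replicates, one-sided 0.05) gives:

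| Outcome, share of factor | Site + period | + three demographics unrelated to the factor | + the factor |
|---|---|---|---|
| BUP, 20% to 30% | 22% | 23% | 5.0% |
| BUP, 20% to 40% | 56% | 56% | 5.1% |
| Engagement, 20% to 30% | 29% | 28% | 4.9% |
| Engagement, 20% to 40% | 66% | 65% | 5.3% |

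Over the wider range the formula gives 8%–99% for BUP at baseline 15%, 7%–79% at baseline 5%, and 8%–99.8% for engagement.

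**Step 4: the planned model with calendar time.** A step change at the switch still loads on period, but the standard error is larger by √4.5 = 2.1 to √7.8 = 2.8. For BUP at +10 points, z falls from 0.91 to 0.43–0.33 and the false-positive rate to about 11%–9%; for engagement (z = 1.03) to about 12%–10%. The 22% and 29% therefore belong to the final model.

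**The case against.** **The plan has other protections.** This stands in part. Protocol 7.3 requires sequential recruitment rather than convenience sampling. Protocol 9.1.1 has staff screen from the ED log and record exclusions with reasons. SAP 4.1.1 tabulates screen failures by period, and SAP 7.7 commits to a descriptive comparison of cohorts. Eligibility criteria are the same in both periods. It would be wrong to infer that 5.1 is the only safeguard. But these measures restrain recruiters or display a shift; they do not stop a change in who comes to the ED, and none changes the model. Protocol 12.14.2 lets further covariates be considered but commits to none, and SAP 7.5.1 does not repeat it. The SAP 7.5.2 sensitivity analyses concern only the COVID-19 pause.

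**The mechanism is inferred.** This stands. Marketing is described as raising awareness and prompting discussion between patients and providers. Nothing says that it brings treatment-seekers to the ED, that treatment-seeking predicts either outcome, or that any shift favours IF.

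**A shift caused by marketing is part of IF.** This also stands. Marketing is a listed IF component (Protocol Table 1) and the aim is the effect of the whole bundle. Only a change from recruiter behaviour or unrelated drift is plain confounding.

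**The size depends on the assumptions.** A reader might infer that case mix could supply half or more of the planned effect. With BUP given to 40–50% of treatment-seekers and 5% of others, a rise in seekers from 20% to 35% adds 5.3–6.8 points (0.15 × 0.35 to 0.15 × 0.45). That implies an odds ratio of about 13–19 and is set against only the smaller planned difference, 15% to 25%. The documents support neither input. At OR 8, reproducing 15% to 25% in full needs the share to go from 20% to about 50%.

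**Conclusion.** The concern holds as unprotected exposure to bias, not as bias shown. Neither the planned nor the final primary model adjusts for case mix, and no committed supportive model does so beyond stepwise sex, race and ethnicity. If a factor with OR 4 gained 10 points of share and IF did nothing, the final model would show about 2 points on BUP (15% to 17.2%) and 3 on engagement (25% to 27.9%), with false-positive rates of about 22% and 29% against a nominal 5%. Those sizes rest on an assumed share, shift and odds ratio. A reader might go further and conclude that the reported IF effect is a case-mix artefact; the documents do not support that, since they report no shift. The point warrants a supportive analysis and does not overturn the primary result.

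**What to change.** 1. In SAP 7.5, and beside the final model in the Revised SAP, add one supportive model per primary outcome with forced, not stepwise, terms for reason for index visit (treatment-seeking, overdose, other), OUD severity, fentanyl-positive and stimulant-positive urine, insurance and age. Report the risk difference standardised to the pooled case mix beside the unadjusted one.
2. In SAP 5.1, delete the rule to test when differences are suspected, and tabulate reason for visit and insurance by period, adding those rows to Table 11.

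The cost is SAP wording, two table rows and one extra model per outcome on data already collected. The downside is that reason for visit may lie partly on IF's own path through marketing, so the adjusted figure should be read as practice change at fixed case mix and must not replace the primary result. The Revised SAP already reports results, so a model added now must be dated and labelled post hoc.
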